 - m. Number and proportion of screened negative pediatric contacts eligible for preventive therapy
 - n. Number and proportion of pediatric patients started on preventive therapy of those who are eligible for preventive therapy
 - o. Number and proportion of pediatric patients on preventive treatment who completed therapy

2. Secondary Objectives

- a. To determine the effect of the CaP TB project on the above TB service indicators and clinical outcomes compared to baseline (standard of care) in a subset of project sites.
- b. Utilize the evidence generated from this program evaluation to support strategic recommendations to improve pediatric TB care.

- c. Utilize clinical aggregated data generated by this study to inform cost-effectiveness analysis of pediatric TB interventions implemented by CaP TB project that can contribute informing childhood TB planning and strategic allocation of financial resources
- d. Utilize evidence generated from this program to assess the impact of measures enforced to control the COVID -19 pandemic on accessibility and availability of pediatric TB services

III. Expected Outcomes of the Study

The main expected outcome of CaP TB project is to reduce morbidity and mortality associated with pediatric TB^{xxx} by reducing the pediatric TB diagnostic and treatment gap, increasing coverage of quality assured TB treatments, as well as scale up of TB preventive therapy through innovative models of care for pediatric TB that focus on integration and decentralization. We expect that this program evaluation will document a positive impact of the CaP TB model, with estimated two-fold increase in case detection and four-fold increase in pediatric patients started on TB preventive therapy based on project target estimates. The evaluation of the CaP TB project will allow for dissemination of the results and further uptake of proven models by other countries.

IV. Study Design

We are planning a pre-/post-project (quasi experimental) intervention evaluation. The population will include all pediatric patients (0-14 years of age) who present to a CaP TB project site in any of the 10 countries and receive TB services (including screening, diagnosis and treatment for active TB, and provision of TB preventive therapy).

A. Methodology

[figure not shown]
1. Description of the CaP TB Project

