2. Country-Level Activities

EGPAF and SAATHII have strong expertise in implementing innovative service delivery models and will provide training, supportive supervision, job aids, and standard operating procedures (SOPs) to health care workers who are engaged in the care of pediatric patients at CaP TB facilities. The goal of these activities is to support the strengthened uptake of current recommendations on TB screening, diagnosis and treatment as well as allow for decentralization and integration of pediatric TB care. CaP TB will also provide training to strengthen completion of TB registers, and may develop other M&E tools to improve the documentation of pediatric TB. EGPAF and SAATHII will also assess and provide SOPs and infrastructure upgrades to improve infection control. EGPAF and SAATHII will support innovations to improve service delivery including creating facility-specific TB champions to monitor service quality, regular performance feedback to facilities, and work with civil society to identify areas to improve care.

Specific packages of activities will vary by country and will be determined based on (1) national policies and guidelines; (2) planned and existing activities supported through other efforts; and (3) country-specific pediatric TB burden and barriers and bottlenecks. For Country Submission- refer to country specifics.

In general, country-level activities will include:

- Decentralizing and integrating delivery of pediatric TB care (diagnosis, treatment (where feasible), and prevention) into MNCH, HIV, nutrition and other key pediatric entry points at the facility level;
- Supporting community-level contact tracing and screening of pediatric contacts for index patients with active TB and where feasible according to MOH guidance, initiation of preventative TB therapy at the community level;
- Documenting and generating evidence for innovative models of care through M&E;
- Strengthening data systems through support for improved use of current registers as well as introduction of new data tools where gaps exist (e.g. for tracking of TB preventative therapy completion in some countries);
- Supporting rapid uptake through trainings, site monitoring and mentorship and strengthening sample transport and referral systems of new diagnostics and medicines that are included in WHO guidelines and are either included in country guidelines or are in the process of being incorporated into national guidance, such as:

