- Screening for TB (clinical symptoms or signs)
- Receiving services (such as contact tracing) as a result of being a contact of a TB index case
- Clinical diagnostic assessment for TB
- Microbiologic diagnostic assessment for TB
- Treatment for active TB
- TB preventive therapy

Data collection of pre-intervention baseline data will take place prior to the start of CapTB interventions or immediately after, ensuring that the calculated data abstraction period does not overlap with any of the early project interventions. Data collection in each site may last up to 4 days and in some cases data collection may last several days longer.

VI. Evaluation Design and Methods

CaP TB implementation data will be collected by project-specific data collection tools and/or from existing registers. Whenever possible, the CaP TB data collection will use existing site level data collection tools to gather the data for the project. However, where such tools do not exist or the tools have gaps to capture all the necessary indicators, we will introduce project-specific data collection tools, the Pediatric TB Intensified Case Finding Screening Tool (ICF tool), the CaP TB Pediatric TB Form and any other form that may evolve as we learn lessons from project implementation.

Use of project-specific data collection tools

As part of the CaP TB intervention, healthcare workers will fill out a Pediatric TB Intensified Case Finding Screening Tool (ICF tool). This tool has no identifying information and will provide information on 1) number of children screened for TB in each healthcare entry point (e.g. pediatric ward, outpatient department, MNCH clinic, and nutrition clinic); 2) sex of the child; 3) age of the child; 4) if the child has any signs of symptoms concerning for TB (according to WHO guidance); 5) if the child is a contact of a TB case; and 6) the date of screening. The forms are also color coded according to the healthcare entry points where children are seen (White= MCH/PMTCT; Blue= outpatient department; Pink= Nutrition; Yellow= Pediatric Ward, Other=to be decided). See Attachment: Pediatric TB Intensified Case Finding Screening Tool.

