Number and proportion of children screened for TB among clinic attendees	TB screening logbooks/registers	Pediatric TB Intensified Case Finding Screening Tools and Clinic attendance registers And/or TB screening logbooks/registers
Number and proportion of presumptive pediatric TB cases identified among children screened for TB	TB screening logbooks/registers Presumptive TB registers	CaP TB Pediatric TB Form And/or TB screening logbooks/registers
Number and proportion of presumptive TB cases referred for lab-based TB diagnosis	TB screening logbooks/registers or Presumptive TB registers	CaP TB Pediatric TB Form And/or TB screening logbooks/registers, Presumptive TB registers
Number and proportion of pediatric (0-14 years) presumptive TB cases who are tested with Xpert	TB diagnostic logbooks/registers or Xpert logbooks/registers	CaP TB Pediatric TB Form And/or TB diagnostic logbooks/registers or Xpert logbooks/registers
Number and proportion of pediatric TB cases diagnosed with active TB disease among presumptive TB cases	Presumptive TB registers and TB registers	CaP TB Pediatric TB Form And/or TB registers/logbooks
Time between when a child is identified as a presumptive TB case and when the child is diagnosed with TB	Presumptive TB registers, TB registers/logbooks	CaP TB Pediatric TB Form And/or Presumptive TB registers, TB registers/logbooks
Number and proportion of pediatric TB cases started on DS-TB treatment	TB registers/logbooks	CaP TB Pediatric TB Form And/or TB registers/logbooks
Time between when a child is identified as a presumptive TB case and when the child is initiated on TB treatment	Presumptive TB registers, TB registers/logbooks	CaP TB Pediatric TB Form And/or

		Presumptive TB registers, TB registers/logbooks
Number and proportion of pediatric DS-TB cases who achieve treatment success	TB treatment register	TB treatment register
Number and proportion of all TB index cases for whom successful contact tracing has been done	TB registers/logbooks Contact tracing forms and registers if available	CaP TB Pediatric TB Form and TB register And/or TB registers/logbooks Contact tracing forms and registers if available
Number and proportion of pediatric household contacts who are negative to TB screening	TB registers/logbooks Contact tracing forms and registers if available	CaP TB Pediatric TB Form And/or TB registers/logbooks Contact tracing forms and registers if available

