Number and proportion of screened negative pediatric contacts eligible for preventive therapy	TB registers/logbooks Contact tracing forms and registers if available	CaP TB Pediatric TB Form And/or TB registers/logbooks Contact tracing forms and registers if available
Number and proportion of pediatric patients started on preventive therapy of those who are eligible for preventive therapy	TB preventive therapy register	CaP TB Pediatric TB Form And/or TB preventive therapy register
Number and proportion of pediatric patients on preventive treatment who completed therapy	TB preventive therapy register	TB preventive therapy register And/or TB preventive therapy register

B. Table 2. Additional Indicator Outcomes and Data Sources

Additional data will be collected during the pre-intervention phase and will be used to estimate project targets. This table presents an example of data sources. Specific data sources may vary

from country to country. All country-specific data sources will be approved for data extraction by the local IRB.

Primary Outcomes	Data source
Number of HIV positive children (0-14 years) in care	HIV clinic register
Number of adult TB cases notified (disaggregated by age, sex, type of TB [PTB smear positive, PTB smear negative; EPTB], new or previously treated case, DS or MDRTB case)	TB treatment Register
Number of pediatric household contacts recorded for each adult TB case (disaggregated by age, sex)	TB register or TB contact tracing register In countries where information is not recorded in the above described register, there might be the need to extract this information from a sample of patient forms
Number of HIV positive pregnant women in care (disaggregated by age)	PMTCT register
Number of HIV+/TB pregnant women (disaggregated by age, type of TB [PTB smear positive, PTB smear negative; EPTB], new or previously treated case, DS or MDRTB case)	PMTCT register

VII. Use of data generated through CaP TB program evaluation to perform secondary analysis

A. Use of CaP TB Program evaluation data to inform cost-effectiveness analysis

Data documenting the costs and cost-effectiveness of pediatric TB interventions remains limited^{xxxv, xxxvi}, and this represents one of the contributing factors to the under-funding of childhood TB programming^{xxxvii}. The data generated through the TIPPI evaluation are well placed to inform the cost-effectiveness assessment of the package of pediatric TB interventions implemented under the CaP TB project.

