Following the completion of the evaluation and all analyses, paper-based documents for all data collection activities, including the second yellow copy of the CaP TB form, will be stored for three years and then destroyed. The first white copy of the form will stay at requesting health facilities and will be kept according to local regulations. Key patient information from the CaP TB form will also have to be recorded by the site personnel on NTP forms, registers, and patient files.

XI. Ethical Considerations

A. IRB Review

This protocol will be reviewed by an Institutional Review Board (IRB) in the US and an ethical review committee in each of the ten project countries. The local ethics committees will also receive country-specific details about the evaluation. Participants will not be compensated.

B. Ethics Training

All EGPAF data collectors, monitoring and evaluation staff and management staff will be trained in research ethics prior to starting data abstraction and collection activities.

C. Conflict of Interest

The PIs and co-investigators listed on this protocol have no affiliations with or involvement in any organization or entity with any financial interest (such as honoraria, grants, employment, consultancies), or non-financial interest (such as personal or professional relationships, affiliations, knowledge or beliefs) in the subject matter or materials discussed in this protocol.

D. Informed Consent

The pre- and post- intervention, quantitative data abstraction is limited to data that are routinely documented as part of standard medical care and/or program services. The data will be abstracted from CaP TB project forms (Pediatric TB Intensified Case Finding Screening Tool or CaP TB Pediatric TB Form), registers, logbooks or rarely, patient files. With the exception of the patient ID (if any), the TB treatment register number or the Preventative Therapy register number, no identifying information will be collected. This information will be encrypted before upload to the database. Only the health facility staff will have access to the identification number that links the ID or treatment register number to the child's name and other identifiable patient information such as caregiver's name and address.

A waiver of informed consent is being requested for all patients whose data will be abstracted for the following reasons according to the U.S. Code of Federal Regulations (CFR 46.116(d))^{XLII}:

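### For 12 of the 14 Table 1 indicators the data source may change between baseline and post-intervention, so better recording can appear as a CaP TB effect

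*Combined protocol and SAP*

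**What the plan says.** The design is uncontrolled. Section IV states: "We are planning a pre-/post-project (quasi experimental) intervention evaluation". Secondary objective (a) is the effect compared with baseline in a subset of sites. Section III expects case detection to double and preventive therapy starts to rise four-fold.

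Table 1 (Section VI.A) lists sources by period:
- **Diagnosed with active TB:** baseline "Presumptive TB registers and TB registers"; post-intervention "CaP TB Pediatric TB Form And/or TB registers/logbooks".
- **Preventive therapy started:** baseline, the preventive therapy register; post-intervention "CaP TB Pediatric TB Form And/or TB preventive therapy register".
- **Children screened:** baseline, screening logbooks or registers; post-intervention "Pediatric TB Intensified Case Finding Screening Tools and Clinic attendance registers And/or TB screening logbooks/registers".
- **DS-TB treatment success and preventive therapy completion:** the register in both periods.

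Section VI explains when the new tools come in: "where such tools do not exist or the tools have gaps to capture all the necessary indicators, we will introduce project-specific data collection tools". It returns to registers after launch if the form is not completed or the country does not support the tools. Section IV.A.2 lists among the project activities "Strengthening data systems through support for improved use of current registers as well as introduction of new data tools where gaps exist".

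Section IX plans a ratio or difference of proportions with Z-tests, and a t-test or rank test for turnaround times. The only bias named in the design rationale (Section V) is secular trend.

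**The concern.** When the measuring instrument can change along with the intervention, a before/after difference mixes two things: children newly reached, and children who would have been cared for anyway but are now written down. Section IV.A.1 hypothesises more case detection and care delivery. Recording a child who was already being treated is neither.

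The documents themselves give reason to expect unequal capture. Tools are added where existing ones fall short. Section V.A accepts that some baseline data will not be found in registers or logbooks. Section VI has a project data collector follow up missing preventive therapy initiation dates, and no such step is described for baseline. Long duration and many sites, which Section V offers as mitigation for secular trends, do nothing about a change in measurement.

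At stake are secondary objective (a), the two headline increases, and the cost-effectiveness analysis in Section VII.A, which uses pre- and post-period monthly site rates for notifications, treatment starts and preventive therapy starts.

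**Working it through.** **Nothing to reproduce.** The plan states no recording completeness, sample size or significance level. All capture values below are assumptions chosen to show a range.

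**Step 1. Count the indicators.** Table 1 has 14 rows. Two (treatment success, preventive therapy completion) keep the register as source in both periods. In the other 14 − 2 = 12, the post-intervention cell adds the CaP TB Form or the ICF tool. Of the four key indicators in Section V.A, cases diagnosed and preventive therapy started can change source; the other two do not.

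**Step 2. Counts.** Let c0 and c1 be the shares of true events recorded at baseline and post-intervention. Then apparent ratio = true ratio × c1/c0. With no true change (true ratio 1):
- 90% then 95%: 0.95/0.90 = 1.06
- 80% then 95%: 0.95/0.80 = 1.19
- 70% then 95%: 0.95/0.70 = 1.36

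Read the other way, an observed 2.0-fold rise would be a true 2 × 0.80/0.95 = 1.68-fold or 2 × 0.70/0.95 = 1.47-fold rise. An observed 4.0-fold rise would be 4 × 0.80/0.95 = 3.37-fold or 4 × 0.70/0.95 = 2.95-fold.

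**Step 3. Proportions.** Here the apparent ratio = true ratio × (numerator c1/c0) ÷ (denominator c1/c0). With no true change:
- numerator 80% to 95%, denominator complete in both periods: 1.19
- both 80% to 95%: 1.19/1.19 = 1.00
- numerator 80% to 95%, denominator 70% to 95%: 1.1875/1.3571 = 0.875

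So the sign depends on which part of the fraction gains more. Better listing of presumptive or eligible children can lower the proportion diagnosed or started. For turnaround times the documents give no basis for a direction.

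**Step 4. The planned Z-test.** Table 3 expects at least 5 presumptive children per clinic at up to 200 sites, about 5 × 200 = 1,000. Assume 1,000 records per period, complete denominators, two-sided alpha 0.05 and no true change. The chance of a significant apparent improvement is then:

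| True proportion | Capture 90% then 95% | Capture 80% then 95% |
|---|---|---|
| 50% | 20% | 92% |
| 20% | 8% | 42% |

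These figures ignore clustering by site and, by Step 3, do not apply where denominators also gain.

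**Step 5. Look for a safeguard.** Quality assurance (Section IX.A) checks forms and database entries for completeness and agreement; it does not measure how complete baseline registers were. No common-source analysis, form-versus-register comparison or sensitivity analysis is planned.

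**The case against.** Several points on the other side stand.

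- A reader might infer that all post-intervention outcomes come from new forms. They do not. The cells say form and/or registers, Table 1 is labelled an example that varies by country, and two of the four key indicators keep the same register. This narrows the scope, but it also means the source may differ by country and site with no stated rule.
- A reader might infer that the bias favours the project throughout. Step 3 shows this is clear for counts only.
- A reader might push the assumed capture to 50% then 100%, which gives 2.0 and would explain the whole case-detection target. Nothing in the documents supports that pair.
- A reader might infer passive recording before and active recording after. Baseline is also active: trained collectors search registers, logs and some patient files across all pediatric entry points (Section V.A).
- A reader might infer that a like-for-like source exists for every indicator. Section X says that key form information "will also have to be recorded by the site personnel on NTP forms, registers, and patient files", but this is not every item, and Section V.A expects gaps at baseline. Where forms are used, Section VI describes continued extraction only from the treatment and preventive therapy registers. Presumptive registers and Xpert logbooks are not shown to be abstracted alongside forms.
- Register completion is itself strengthened (Section IV.A.2), so a same-register comparison is not free of recording gain either.

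The last two points limit what any remedy can achieve. None removes the need for a source rule.

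**Conclusion.** The concern holds in a limited form. For 12 of 14 indicators, including the two behind the expected two-fold and four-fold increases, the plan allows the source to change between periods and then compares the periods without adjustment. A recording gain can therefore be reported as a programme effect. For counts the bias is upward: 1.19 and 1.36 at the two illustrative capture pairs, both assumed. For proportions and turnaround times the direction is open. Treatment success and preventive therapy completion do not change source, though register strengthening can still affect them.

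The documents do not show that the expected increases are an artefact. They show that the planned analysis cannot separate recording from care.

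**What to change.** In Section IX:

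1. State that the pre/post comparison of children started on DS-TB treatment and children started on preventive therapy uses counts from the TB treatment register and the preventive therapy register in both periods, at sites with data for both. Express them per site-month, because the periods differ in length; Section VII.A already uses monthly site rates and this site restriction. Report form-based post-period figures alongside.
2. For the other indicators, including cases diagnosed, use the same source in both periods where it was abstracted in both. Otherwise report them descriptively with a source-by-period table, and do not test them as an effect of CaP TB.
3. State that, because registers are strengthened, a same-source comparison removes only part of the recording effect.

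The treatment register should not supply both diagnosed and started: that would push the proportion started towards 100% and lose children diagnosed but never started. A check on missing treatment or preventive therapy outcomes is no substitute, since those indicators do not change source. Nor is a count of Xpert-positive children, because Table 1 lists children tested, not positives.

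**Cost.** Mostly wording and a further analysis, since collectors already visit both registers after launch. This assumes that their extraction covers all children aged 0-14 started, not only those with a form; if not, a register count is needed at the baseline sites (up to 200). Register counts may be lower than form counts, so the estimated effect may be smaller, and some indicators lose a formal pre/post test.

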The CaP TB model represents one potential way of improving the care of pediatric TB. However, it will be important to measure this model's effect on key service and clinical indicators related to pediatric TB in order to help guide future programming and resource prioritization. In order to describe the effect of the CaP TB model on these indicators, we plan a pre- and post-intervention evaluation in all project countries. We have chosen this pragmatic approach to allow us to compare the outcomes after we begin CaP TB implementation with the same indicators baseline (pre-implementation). This can help us define the effect of our specific project on the project evaluation indicators. As this is an evaluation of program implementation a randomized approach would not be feasible for both programmatic and financial reasons. We do recognize that secular trends may affect our outcomes, but we feel that the duration of the evaluation (over several years) and the large size and multi-country nature will help to mitigate that risk.

A. Pre-intervention Evaluation- Baseline assessment

In each country, a pre-intervention retrospective data collection will take place in a sub-set of project sites.

This data collection activity will:

1. Capture data that will answer the TB service indicators and clinical outcomes listed in the primary objectives.
2. Capture key data points that will be needed to estimate project targets

The main objectives of the CaP TB interventions are:

- to increase the number of children diagnosed with TB
- To increase the number of children who are started on and complete DS-TB treatment
- To increase the number of children who are started on and complete TB preventive therapy.

Key indicators that will be used to monitor project interventions and assess impact will therefore be:

- Number of pediatric cases diagnosed with active TB disease
- Number and proportion of pediatric DS-TB cases who achieve treatment success
- Number and proportion of pediatric patients started on preventive therapy of those who are eligible for preventive therapy
- Number and proportion of pediatric patients on preventive treatment who completed therapy

Data sources for these indicators during the pre-intervention phase are described in Table 1.

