To this aim, EGPAF will sub-contract University of Sheffield, key leader in childhood TB health economic modelling, to perform a cost-effectiveness analysis (CEA). The resulting effects estimates will be based on routinely collected project intervention country-level aggregates from key indicators describing the cascade of care, as well facility-level data for the comparison of the pre- and post- project intervention phase. All data to be used will have already been collected through TIPPI Pre-Intervention evaluation (described in section V, subsection A) and CaP-TB implementation evaluation (described in section V, subsection I).

Only aggregated clinical data will be shared with University of Sheffield and thus considered for the CEA analysis, as described below:

- i. Averaged monthly rates per site (including absolute numerator and denominator) of pediatric (children aged 0-14 years) TB notifications, DS-TB initiations, and PT initiations for a subset of sites for which both baseline and prospective data have already been collected (restricting to sites where data on both periods are available).
- ii. Country-aggregated project intervention numbers of: a) Children screened for TB, b) Children identified as presumptive TB, c) Children with presumptive TB tested with Xpert, d) Children diagnosed with TB, e) Children treated for DS-TB, f) All TB index cases for whom successful contact tracing has been done, g) Children started on TB Preventive Therapy (disaggregated by HIV and Contact investigation entry points), and h) Sites contributing to the country-level dataset.

All patient-level indicators mentioned in points i and ii above are included in Table 1. The cost-effectiveness analysis will use pre-intervention and project intervention data, with the potential for sub-analysis of shorter targeted period during the intervention phase.

The final cost-effectiveness analysis outcomes are expected to be reported by country, and individual countries will be identified to allow to use context-specific results to inform decision-making.

The costs will be estimated as follows:

- Core health services costs will be derived from published literature.
- CaP TB intervention costs will be estimated based on EGPAF CaP TB budgets and expenditure data from EGPAF's financial system.
- EGPAF country team staff will assist in allocating cost items to specific activities within the CaPTB cascade of service delivery.

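### For treatment and preventive therapy, the project data listed for the cost-effectiveness analysis stop at starts, leaving out the treatment success and completion that the project plans to measure

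*Combined protocol and SAP*

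**What the plan says.** Section VII.A describes the analysis that the sponsor will subcontract to an academic modelling group. It states: "Only aggregated clinical data will be shared with University of Sheffield and thus considered for the CEA analysis, as described below". Two lists follow.

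- List (i) is the only one with both periods, for sites that have baseline and prospective data. It holds "Averaged monthly rates per site (including absolute numerator and denominator) of pediatric (children aged 0-14 years) TB notifications, DS-TB initiations, and PT initiations".
- List (ii) holds country totals for the project period: children screened, presumptive, tested with Xpert and diagnosed, then "e) Children treated for DS-TB, f) All TB index cases for whom successful contact tracing has been done", then "g) Children started on TB Preventive Therapy (disaggregated by HIV and Contact investigation entry points", and the number of contributing sites.

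The same section says "The resulting effects estimates will be based on routinely collected project intervention country-level aggregates from key indicators describing the cascade of care", together with facility-level data for the pre/post comparison. It also says "All patient-level indicators mentioned in points i and ii above are included in Table 1". Published literature is named as a source only for core health service costs. Project costs come from the sponsor's budgets and expenditure.

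Elsewhere the plan gives outcomes more weight. Section V.A lists among the main objectives "To increase the number of children who are started on and complete TB preventive therapy", with a parallel objective for DS-TB treatment. Treatment success and PT completion are two of its four key indicators. It also explains that the baseline window was set so that completion could be measured for both kinds of course. Table 1 gives register sources for both indicators, before and after the intervention.

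**The concern.** Health benefit depends largely on the course a child receives, while cost begins at the start of that course. A programme that greatly expands starts, partly in decentralised and community settings, could raise or lower the share of children who finish. The country activities in section IV.A.2 include treatment-adherence support such as SMS reminders. That spending enters the cost side through project expenditure, yet any gain in completion it buys has no route into the project-based effect. A fall in completion during scale-up would be equally invisible.

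Section VII.A intends results by country, so that context-specific figures can inform decisions. A country whose completion differs from the value used in the model would receive a result that ignores what the project observed there.

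**Working it through.** The plan states no figure on this point to reproduce. The check is a comparison of lists, followed by an illustration.

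**Step 1: item check.**

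| Data set | Items | Treatment or PT items | Success or completion items |
|---|---|---|---|
| List (i), site level, pre and post | 3 | DS-TB initiations; PT initiations | 0 of 3 |
| List (ii), country level, project period | 8 | (e) treated for DS-TB; (g) started on PT | 0 of 8 |
| Table 1, planned in both periods | n/a | starts of each | both: treatment success and PT completion |

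Item (e) refers to children treated, not started. Section VII.A says the listed patient-level indicators are in Table 1. The closest indicator there is the number started on DS-TB treatment, since treatment success has its own row. On either reading, (e) is not an outcome, and list (ii) has no baseline period.

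Secondary objective (c) in section II.B and the dissemination text in section XII also mention aggregated data for this analysis. Neither adds to the lists.

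**Step 2: what a model can learn from the lists.** Let F be the fold change in starts, and c0 and c1 the completion (or success) proportions at baseline and during the project. Then

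fold change in completed courses = F × c1 / c0.

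The lists supply F but neither c0 nor c1.

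**Step 3: illustration.** The expected four-fold rise in children started on PT and two-fold rise in case detection come from section III. Applying the two-fold figure to treated cases is my assumption. The documents give no completion or success proportions, so 60% to 90% in each period is also assumed.

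| c0 → c1 | PT, F = 4 | DS-TB, F = 2 |
|---|---|---|
| 90% → 60% | 4 × 0.60/0.90 = 2.67 | 2 × 0.60/0.90 = 1.33 |
| 80% → 60% | 4 × 0.60/0.80 = 3.0 | 2 × 0.60/0.80 = 1.5 |
| unchanged | 4.0 | 2.0 |
| 80% → 90% | 4 × 0.90/0.80 = 4.5 | 2 × 0.90/0.80 = 2.25 |
| 60% → 90% | 4 × 0.90/0.60 = 6.0 | 2 × 0.90/0.60 = 3.0 |

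In counts, section IX projects 52,317 additional PT starts. If the four-fold rise applies to counts, this implies 52,317 / (4 − 1) = 17,439 starts at baseline and 4 × 17,439 = 69,756 with the project. Added completed courses are 69,756 × c1 − 17,439 × c0:

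- 80% in both periods: 41,854
- 90% → 60%: about 26,158
- 60% → 90%: 52,317

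The data in lists (i) and (ii) would be identical in every row.

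**The case against.** The strongest reply is that section VII.A restricts the project data shared, not the model. It does not define the health outcome, and it does not bar success or completion values from outside sources. A benefit parameter expressed per child started may already allow for non-completion, and multiplying it by completion would count the loss twice. This stands, and it rules out a stronger reading. A reader might infer that every start is credited as a full course, which would overstate completed courses by 1/c − 1, or 11% at c = 90% and 67% at c = 60%. The plan does not say this, and those figures apply only if the modellers chose it.

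A reader might also infer that the lists hold nothing but starts. They do not: notifications, screening, presumptive cases, Xpert testing, diagnosis and contact tracing are there too.

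Nor can it be assumed that the missing outcomes are already in hand everywhere for both periods, even though section VII.A says "All data to be used will have already been collected through TIPPI Pre-Intervention evaluation" and the project phase. Section IV.A.2 gives PT completion as its own example of a gap in existing tools. Section V.A warns that some baseline indicators will be unavailable, and Table 1 is presented as an example that may vary by country. Where the project introduces the tracking, better recording could pass for better completion. Table 3 expects as few as five presumptive children per clinic, so site-level success proportions would be unstable. The split of PT by entry point exists only in list (ii).

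Finally, this is a secondary objective, and success and completion are still evaluated as indicators in their own right.

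These arguments limit the fix, mainly at baseline and site level. They do not explain why project-period country totals are left out. Outside values also cannot show the project's own change.

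**Conclusion.** The point holds in limited form. For treatment and preventive therapy, the closed list of project data stops at starts. Two of the four key impact indicators are left out, although the plan intends to abstract both from registers where these exist. Success and completion in the model must then be imported or assumed, and the cost-effectiveness results cannot carry the project's own values or any change from baseline.

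Neither direction nor size can be established from the documents. An effect measured in starts overstates the relative gain in completed courses if completion falls, understates it if completion improves, and is exact if completion is unchanged. The 2.67- to 6.0-fold range for PT rests entirely on the assumed 60% to 90% and on taking the four-fold rise as a rise in starts. The documents do not support a claim that the plan favours the project. The primary indicators are unaffected. This is a worthwhile, low-cost improvement to an analysis meant to inform country decisions.

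**What to change.** 1. Add to list (ii), by country for the project period, numerators and denominators for DS-TB treatment success and for PT completion among children who started. Split PT by HIV and contact-investigation entry point where recorded. Restrict to starts early enough for the outcome to be known. With the six-month courses assumed in section V.A and data collection ending on September 30, 2021, that means starts up to about the end of March 2021.
2. Add the matching baseline values, pooled by country over the paired sites rather than as monthly site rates, and only where baseline registers recorded the outcome. Giving project-period values for the same paired sites makes the comparison like for like.
3. State that the model uses observed values where available and literature values otherwise, naming the source and range. State also that completion is not applied again where a benefit parameter is already per child started.
4. Include a sensitivity analysis holding completion and success equal in both periods, because improved recording could look like improved completion.

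Cost: three outcomes (success, and PT completion in two strata), each with a numerator and a denominator, make 6 columns per set. There are 6 for step 1, 12 with baseline, and 18 with project-period values for the paired sites. No new data collection and no sharing of patient-level data is needed, but the data-sharing list must be amended. The drawbacks are unknown outcomes for late starters and patchy baseline PT completion in some countries.
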